#### **Retrospective analysis of patients who received a fully artificial heart.**

The duration of the intervention in each group will be 72 hours. Each Jaftron / CytoSorb Removal Column can be used within 24 hours, so all patients in 2 groups use 3 filters during the study.

Researchers will collect demographic, clinical and laboratory data from patients before, during and after surgery.

The incidence of early cellular or humoral rejection, the duration of ventilation, intensive care and hospital stay, the use of vasopressors and inotropes in the perioperative period, and the incidence of perioperative complications and survivals will be documented.

The level of cytokines (IL-1, IL-6, IL-8, IL-10, tumor necrosis factor alpha) and complements will be determined before, during and after the use of the extracorporeal life support system for heart and pulmonary failure; surgery on the aortic arch, patients on mechanical circulatory support, if investigators find a corresponding difference between the two groups in terms of clinical variables.

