#### **Study design.**

Study type: interventional (clinical study)

Set of participants: 100 participants

Distribution: randomized

Interventional model: parallel

Masking: no

Primary Goal: Treatment

| Intervention team (1 group)  | Intervention / treatment (device)  |
|--|--|
| Extracorporeal hemoperfusion device will be installed in the device of the extracorporeal life support system for heart failure...
(10 patients)        | HA330 - Jafron Biomedical Co., Ltd., China
- extracorporeal hemocorrection, which is based on the removal of cytokines from whole blood by sorption on a special hemoabsorbent due to the peculiarities of its porous structure and inner surface, which is indicated in conditions where cytokine levels are extremely elevated. |
| Extracorporeal hemoperfusion device will be installed in the device of the extracorporeal life support system for pulmonary failure
(10 patients).      | HA330 - Jafron Biomedical Co., Ltd., China
- extracorporeal hemocorrection, which is based on the removal of cytokines from whole blood by sorption on a special hemoabsorbent due to the peculiarities of its porous structure and inner surface, which is indicated in conditions where cytokine levels are extremely elevated. |
| An extracorporeal hemoperfusion device will be installed in patients before / during the implantation of a left ventricular assist device
(5 patients). | HA330 - Jafron Biomedical Co., Ltd., China
- extracorporeal hemocorrection, which is based on the removal of cytokines from whole blood by sorption on a special hemoabsorbent due to the peculiarities of its porous structure and inner surface, which is indicated in conditions where cytokine levels are extremely elevated. |
| An extracorporeal hemoperfusion device will  | HA330 - Jafron Biomedical Co., Ltd., China   |

|   |  |
|---|--|
| be installed in patients during operations with prolonged cardiopulmonary bypass, hypothermia and circulatory arrest. (25 patients).  | - extracorporeal hemocorrection, which is based on the removal of cytokines from whole blood by sorption on a special hemoadsorbent due to the peculiarities of its porous structure and inner surface, which is indicated in conditions where cytokine levels are extremely elevated. |
| Intervention team (2 groups)   |  |

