### Performance evaluation criterias

| Extracorporeal life support system with pulmonary and / or heart failure |
|---|
| Primary results  |

|                          |   |
|--------------------------|---|
| 1                 | Cytokine response [Time: 24-48 hours]

The level of pro- and anti-inflammatory cytokines (IL-1, IL-6, IL-8, IL-10, tumor alpha-factor) before the implantation, 2 hours after the start of ECMO support, explantation of ECMO, 24 hours after explantation of ECMO.     |
| 2                 | SOFA-Score [Time Frame: 24, 48, 72 hours]

Sequential Organ Failure Assessment Score at 24, 48, 72 h (values from 6 to 24, where the higher values explain higher disease severity)   |
| 3                 | Difference of mean arterial pressure [Time Frame: 24, 48, 72 hours]

Comparison of mean arterial pressure at 24, 48, 72 hours between between two interventions (CytoSorb and Jafron)   |
| 4                 | Difference of CVP [Time Frame: 24, 48, 72 hours]

Comparison of CVP at 24, 48, 72 hours between between two interventions (CytoSorb and Jafron)   |
| 5                 | Serum lactate [ Time Frame: 24, 48, 72 hours ]

Level of serum lactate at 24, 48, 72 h  |
| 6                 | 
 
Days on ventilator, vasopressor and renal replacement therapy [ Time Frame: until day 30 post-surgery ]
 

Total days on ventilator, vasopressor and renal replacement therapy within 30 days post-surgery will be assessed |
| 7                 | Doses of vasopressors and / or inotropes ( $\mu\text{g} / \text{h} / \text{kg}$ bodyweight) [Time: first 72 hours]  |
| Secondary results |   |
| 1                 | Inflammatory response - The level of C-reactive protein (CRP) [Time: 24-48 hours]

The level of C-reactive protein (CRP) before the start of ECMO, 2 hours after the implantation of ECMO, during ECMO, 24 hours after ECMO explantation.                        |
| 2                 | Inflammatory response - The level of leukocytes [Time: 24-48 hours]

The level of leukocytes before the start of ECMO, 2 hours after the implantation of ECMO, during ECMO, 24 hours after ECMO explantation.   |

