| 3                 | Inflammatory response - The level of procalcitonin [Time: 24-48 hours]

The level of procalcitonin before the start of ECMO, 2 hours after the implantation of ECMO, during ECMO, 24 hours after ECMO explantation.   |
| 4                 | Level of leukocyte [Time: 24-48 hours]

Level of leukocyte cells in the bloodstream at 24, 48 hours.  |

|                          |  |
|--------------------------|--|
| 5                 | Application and dosage of vasopressors [Deadline: first 48 hours]
Incidence of application and level of dosage of vasopressors on days 2 and 3 after surgery; |
| 6                 | Application and dosage of inotropes [Deadline: first 48 hours]
Incidence of application and level of dosage of inotropes on days 2 and 3 after surgery;       |
| Long-term results |  |
| 1                 | Length of stay in the intensive care unit [Duration: first 48 hours]   |
| 2                 | Length of hospital stay [Term: up to 1 month];   |
| 3                 | 30 day survival rate.  |

| Patients with left ventricular assist device implantation |  |
|--|--|
| Primary results   |  |
| 1   | Difference of Cytokine response [Time: 24-48 hours]
Level of pro- and anti-inflammatory cytokines (IL-1, IL-6, IL-8, IL-10, tumor necrosis factor-alfa, procalcitonin)  |
| 2   | Doses of vasopressors and / or inotropes ( $\mu$ g / h / kg bodyweight)
[Deadline: first 72 hours]  |
| 3   | Renal function [Time: first 72 hours] creatinine level   |
| 4   | Lactate level [Time: first 72 hours]   |
| Secondary results   |  |
| 1   | Inflammatory response - The level of C-reactive protein (CRP) [Time: 24-48 hours]
The level of C-reactive protein (CRP) before the start of the operation, 2 hours after the start of the operation, when the operation is turned off, 24 hours after the shutdown of the operation |
| 2   | Inflammatory response - The level of leukocytes [Time: 24-48 hours]
The level of leukocytes before the start of the operation, 2 hours after the start of the operation, when the operation is turned off, 24 hours after the shutdown of the operation                             |

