### Statistical research

- 1) statistical data processing
- 2) comparison and analysis of initial data

After data acquisition, statistical analysis will be performed using SPSS Statistics version 22. For quantitative data, the nonparametric Mann-Whitney U test and parametric t-test will be performed, and for qualitative studies, the nonparametric Fisher's exact test and the parametric  $\chi^2$  test will be performed. Also, logistic regression for categorical outcomes and survival analyzes (non-parametric Kaplan-Meyer and parametric Cox regression) will be performed.

**Age:** 18 years and older

**Gender:** All

**Inclusion of healthy volunteers:** Not

| Groups  | Inclusion criteria   | Exclusion criteria  |
|--|---|--|
| Patients on an extracorporeal life support system with heart failure                             | 
 
• Implantation of intravenous ECMO
 
• Hemodynamic support with vasopressors and / or tonics;
 
• Procalcitonin level <math>\geq 1</math> ng / ml;
 
• Invasive hemodynamic monitoring;
 
• Written informed consent.
 
   | 
 
• Age less than 18 years old
 
• Terminal hepatic or renal failure just before the procedure
 
• Patient's written refusal to participate in the study
 
 |
| Patients on an extracorporeal life support system with pulmonary failure                         | 
 
• IV ECMO implantation
 
• High levels of venous and arterial CO2 (CO2 > 50 mmHg),
 
• Low paO2, SvO2, SpO2.
 
• Invasive hemodynamic monitoring;
 
• Written informed consent.
 
                                     | 
 
• Age less than 18 years old
 
• Terminal hepatic or renal failure just before the procedure
 
• Patient's written refusal to participate in the study
 
 |

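### ECMO primary row 6 counts support days to day 30 with no rule for death, so a low total can mean early weaning or early death

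*Combined protocol and SAP*

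**What the plan says.** In Performance evaluation criterias, the ECMO table lists seven primary results. Row 6 is defined as "Total days on ventilator, vasopressor and renal replacement therapy within 30 days post-surgery will be assessed". It has no rule for death, and none is given elsewhere. It does not say whether the three therapies form one count, a sum or three separate totals. It counts from surgery, whereas the ECMO eligibility criteria (for example "IV ECMO implantation") name no operation, so day 0 is undefined.

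Statistical research assigns quantitative data to Mann-Whitney and t-tests. It also names Kaplan-Meier and Cox, without linking either to an outcome. Death appears as a separate long-term result, "30 day survival rate", and survival is among the data to be documented.

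Row 1 is headed "Cytokine response [Time: 24-48 hours". After a pre-implantation sample, its times are "2 hours after the start of ECMO support, explantation of ECMO, 24 hours after explantation of ECMO". The intervention table in Study design places the adsorber in the ECMO circuit: "Extracorporeal hemoperfusion device will be installed in the device of the extracorporeal life support system for pulmonary failure". The text under the heading on the fully artificial heart states "The duration of the intervention in each group will be 72 hours". It also makes cytokine measurement depend on a condition: "if investigators find a corresponding difference between the two groups in terms of clinical variables".

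**The concern.** Death stops the count. A patient who dies on day 3 scores at most 3 days per therapy; a survivor weaned on day 14 scores 14. A raw comparison reads the first as the better result. A primary outcome read this way cannot separate a device that frees patients from support sooner from one under which they die sooner, and if deaths come early it can point to the wrong device.

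Row 1 raises a smaller question. Samples tied to explantation fall at a different time in each patient, the last cannot exist for a patient who dies on ECMO, and the window in the row's heading is not anchored to any event.

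**Working it through.** **Inputs from the documents.** 10 heart-failure plus 10 pulmonary-failure ECMO patients per arm, so 20 per arm and 40 of 100 in all. Horizon 30 days. No alpha, power, effect size or expected mortality is stated, so there is no design figure to reproduce. The 26% to 58% mortality range in section 3 is background for severe acute pulmonary distress syndrome.

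**Direction.** Let m be 30-day mortality, S the survivors' mean support days and D the mean day of death, with patients who die supported until death.

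Mean support days = (1 - m) x S + m x D

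With S and D equal in both arms, the difference (deadlier minus other arm) = (m2 - m1) x (D - S). A negative value favours the deadlier arm.

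**Size, by assumption.** Survivor days are gamma (shape 4, mean 14), rounded and kept within 1-30, giving a realised S of 13.86. Mortality is 26% v 58%, 32% v 52% or 37% v 47%, that is, gaps of 32, 20 and 10 points. For example, D = 5.0 with the 32-point gap gives 0.32 x (5.0 - 13.86) = -2.8 days.

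| Assumed death days | D | Mean difference in days, gaps 32 / 20 / 10 |
|---|---|---|
| 1-9 | 5.0 | -2.8 / -1.8 / -0.9 |
| exponential 10, capped at 30 | 9.99 | -1.2 / -0.8 / -0.4 |
| exponential 14, capped at 30 | 12.81 | -0.3 / -0.2 / -0.1 |
| 1-27 or 10-18 | 14.0 | 0.0 |
| 14-30 | 22.0 | +2.6 / +1.6 / +0.8 |

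**Simulation.** 10,000 trials per setting, 20 per arm, row 6 read as one count, two-sided Mann-Whitney at an assumed 0.05. Each cell gives the share of trials in which the deadlier arm has the lower mean / is significantly favoured.

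| Death days | 26% v 58% | 32% v 52% | 37% v 47% |
|---|---|---|---|
| 1-9 | 91% / 29% | 79% / 14% | 66% / 6% |
| exponential 10 | 70% / 8% | 62% / 6% | 57% / 3% |
| exponential 14 | 55% / 4% | 52% / 4% | 51% / 3% |
| 1-27 or 10-18 | about half / 2% | about half / 2% | about half / 2% |
| 14-30 | 12% / 0.1% | 23% / 0.3% | 36% / 0.9% |

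Repeat runs agree to within about two percentage points. With equal mortality (42% in both arms), the means split about evenly and 2-3% of trials are significant in each direction.

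**Days alive and free of support, death = 0.** Mean = (1 - m) x (30 - 13.86) = (1 - m) x 16.14, giving 11.9 v 6.8, 11.0 v 7.7 and 10.2 v 8.6 days. D has dropped out, so the timing of death no longer matters. The deadlier arm has the better mean in about 4%, 13% and 29% of trials, and is significantly favoured in under 0.1%, about 0.1% and about 0.6%. Right-direction power is about 42%, 19% and 7% to 8%. For 30-day mortality itself it is 41%, 16% and 5% by Fisher's exact test and 53%, 24% and 9% by uncorrected chi-square.

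**Row 1.** If ECMO lasts T hours, the last two samples fall at T and T + 24 from ECMO start. Both lie within 24-48 hours only if T = 24. If the adsorber in the circuit runs its 72 hours, they fall no earlier than 72 and 72 + 24 = 96 hours from adsorber start, both outside. Counted from explantation, the last sample is at 24 hours and lies inside.

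**The case against.** Survival is recorded, 30-day survival is listed and survival methods are planned, so the deaths will be visible. That is true, but it leaves row 6 uncorrected. With 20 per arm the mortality comparison will often miss significance.

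A reader might infer that row 6 will favour the deadlier device. The documents do not support that: the sign depends on D and S, which they do not give, and with late deaths row 6 points the right way. Nor are 26% and 58% the expected rates of two arms. With a 10-point gap, wrong-direction significance is 3% to 6% in the three settings where D < S, against 2-3% by chance. The simulation also uses one reading of row 6, and the effect may differ by component; it is nil for renal replacement therapy in patients who never receive it.

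A death rule could be added without replacing the outcome. That stands: the choice of replacement is partly preference, and it brings no power advantage over testing mortality by chi-square.

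On row 1, a reader might infer a proven contradiction between window and sampling times. Because the window has no stated origin, the mismatch holds only when it is counted from ECMO or adsorber start. Nor can the first two samples be declared sound or unsound, since randomisation and adsorber start are not timed relative to ECMO start.

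**Conclusion.** The point stands, conditionally. Row 6 has no rule for death, and the plan as written compares raw totals, so a low value is ambiguous. The missing rule is certain. The direction and size of any distortion are not: they rest on assumed death times, survivor durations and mortality gaps, on survivors' durations being equal in both arms, on support continuing until death, and on the one-count reading. Under those assumptions the effect ranges from 2.8 days in favour of the deadlier arm to 2.6 days against it. It concerns one of seven primary rows, in 40 of 100 patients, and should be fixed before analysis.

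The row 1 point is secondary: an unanchored window, a final sample that exists only for patients who survive to explantation and beyond, and a primary outcome whose measurement is conditional on a clinical difference. The direction of any resulting bias cannot be determined from the documents.

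**What to change.** **Row 6.** Replace it by days alive and free of ventilation, vasopressors and renal replacement to day 30. A day counts as free only if none of the three is in use; death by day 30 scores 0, the worst value; arms are compared by a rank test. Count from one stated origin common to both arms. Randomisation is suitable because the ECMO criteria name no operation; if the surgical origin is kept, define day 0 and give the reason. Report each component and 30-day mortality alongside. If durations are to be kept, time to coming off each support with death as a competing event is an acceptable alternative.

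No extra patients are needed. Daily on/off records come to at most 40 x 30 x 3 = 3,600 entries, and may be added data collection because only totals are requested now. The new outcome mixes survival with duration, which is why the components must be shown. The gain is protection from a wrong-direction result, not more power.

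**Row 1.** State the origin of the 24-48 hour window and reconcile it with the explantation-timed samples and the 72-hour intervention. Remove the condition on cytokine measurement for this primary outcome. Report by arm how many patients died before each sample. This is wording and reporting only. Samples at 24 and 48 hours from adsorber start would be optional added sampling, taking each ECMO patient from four samples to six if the explantation samples are kept.

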**3. Scientific innovativeness and significance of the program.**

Organ replacement technologies are increasingly being used in the treatment of end-stage pulmonary and heart failure to prolong human life. Severe refractory cardiogenic shock, refractory ventricular arrhythmia, active cardiopulmonary resuscitation in cardiac arrest and acute or decompensated right heart failure, sepsis, pulmonary and multiple organ failure.

Careful patient selection and consideration of possible complications are key factors in optimizing the treatment of patients in this category. Well-defined pathways for medical care to centers capable of delivering heart and lung support replacement therapy (e.g., durable ventricular assist device or heart transplant) is essential to provide high-level patient care, stabilized with extracorporeal life support, and the ability to wean from the device. Ultimately, the concentration of the most complex care in large centers of our country with developed cardiac surgery and anesthetic capabilities can be a way to significantly improve the care of this group of patients.

Despite advances in mechanical ventilation, severe acute pulmonary distress syndrome (APDS) is associated with high morbidity and mortality rates ranging from 26% to 58%. Extracorporeal life sustaining system is a procedure for long-term cardiopulmonary bypass and oxygen saturation of the blood outside the body, used in patients with acutely developed and potentially reversible pulmonary and / or heart failure, whose treatment does not respond to maximum standard therapy. The Heart-Lung Sustaining System is a complex network that provides oxygenation and ventilation and allows the lungs to rest and recover from pulmonary failure while minimizing the iatrogenic lung damage caused by the ventilator. In intensive care in the conditions of an extracorporeal life support system. In 2011, the National Research Center for Cardiac Surgery Non-profit JSC launched a program to provide extracorporeal life support system in Kazakhstan, and in 2016 Non-profit JSC «NRCCS» has entered to the global ELSO register (Extracorporeal Life Support Organization).

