#### **4. Research methods and ethical issues.**

All patients admitted to Non-profit JSC “NRCCS” who meet the study criteria (patients on an extracorporeal life support system, mechanical circulatory support, surgery on the aortic arch) will be included in the study after obtaining a signed informed consent. Participants will be randomized into 2 groups in a 1: 1 division.

**Intervention team # 1** using an extracorporeal hemoperfusion device Jaftron (Zhuhai Jaftron Biomedical, China) (50 patients) in subgroups: A (n = 10) - patients on extracorporeal life support systems with heart failure; B (n = 10) - patients on extracorporeal life support systems with pulmonary failure; C (n = 5) - patients with implantation of a left ventricular accessory device; D (n = 25) - during operations with prolonged artificial circulation, hypothermia and circulatory arrest.

**Intervention team # 2** using extracorporeal cytokine, CytoSorb (CytoSorbents Corporation, Monmouth Junction, NJ, USA) (50 patients) in subgroups: A (n = 10) - patients on extracorporeal life support systems in heart failure; B (n = 10) - patients on extracorporeal life support systems with pulmonary failure; C (n = 5) - patients with implantation of a left ventricular accessory device; D (n = 25) - during operations with prolonged artificial circulation, hypothermia and circulatory arrest.

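### Length of hospital stay has no rule for patients who die before discharge; if observed days are used, more early deaths look like faster recovery

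*Combined protocol and SAP*

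**What the plan says.** In the combined protocol and SAP, the tables under Performance evaluation criterias (ECMO, LVAD, prolonged bypass) each have a block of long-term results. Each block contains "Length of hospital stay [Term: up to 1 month" and, as a separate row, "30 day survival rate". The data-collection text in section 4, under the heading on the retrospective artificial-heart analysis, likewise records "the duration of ventilation, intensive care and hospital stay" as durations and survival as another item.

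Statistical research gives one rule for such variables: "For quantitative data, the nonparametric Mann-Whitney U test and parametric t-test will be performed". It adds that "survival analyzes (non-parametric Kaplan-Meyer and parametric Cox regression) will be performed", but assigns those methods to no outcome and gives no rule for censoring or competing events.

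Nowhere do the documents say whether a stay that ends in death is counted as observed, excluded, set to the maximum, or treated as a competing event.

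**The concern.** A stay can be short because the patient recovered or because the patient died. A test on the raw number of days cannot tell these apart: a death on day 6 ranks ahead of a survivor discharged on day 20. If one device has more early deaths, its stay shortens for that reason alone.

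Excluding deaths does not solve this. The trial is randomised ("Participants will be randomized into 2 groups in a 1: 1 division"), but survivors are a subset defined by what happens after randomisation, so survivors on the two devices need not be comparable.

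Either way, the stay result could favour the wrong device. The results are meant to feed treatment protocols (section 9, Expected results of the program).

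**Working it through.** **Inputs from the documents.** There is no planned figure for stay, or for mortality by arm, to reproduce. The sample size is 2 × (10 + 10 + 5 + 25) = 100, so 50 per arm and 20 per arm in the ECMO table. Section 3 gives background mortality: for severe acute pulmonary distress syndrome "mortality rates ranging from 26% to 58" per cent, and for SIRS, septic shock and sepsis 7, 16 and 40%. Section 9 hopes for a 30% cut in postoperative mortality. Read as relative, this gives 0.7 × 26 = 18.2%, 0.7 × 40 = 28% and 0.7 × 7 = 4.9%.

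**Assumptions (not in the documents).** Survivors' mean stay S and mean day of death d are the same in both arms, with (S, d) = (18, 6) or (22, 8). Mortality is mH in the worse arm and mL in the better arm.

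**Observed days.** Mean stay in an arm is m·d + (1 − m)·S, so the worse arm's mean is shorter by (mH − mL)(S − d). The factor S − d is 12 or 14. At 40% v 28% with (18, 6), for example, the worse arm has 0.40 × 6 + 0.60 × 18 = 13.2 days and the better arm 0.28 × 6 + 0.72 × 18 = 14.64, a difference of 1.44.

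**Days alive and out of hospital to day 30, death scored 0.** The mean is (1 − m)(30 − S), so the worse arm is lower by (mH − mL)(30 − S). The factor 30 − S is 12 or 8.

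| Mortality | Observed stay: worse arm shorter by | Days alive and out: worse arm lower by |
|---|---|---|
| 7% v 4.9% | 0.021 × 12 to 14 = 0.25 to 0.29 | 0.021 × 8 to 12 = 0.17 to 0.25 |
| 26% v 18.2% | 0.078 × 12 to 14 = 0.94 to 1.09 | 0.078 × 8 to 12 = 0.62 to 0.94 |
| 40% v 28% | 0.12 × 12 to 14 = 1.44 to 1.68 | 0.12 × 8 to 12 = 0.96 to 1.44 |

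The first measure favours the arm with more deaths and the second does not. Crossing the assumed pairs widens S − d to 10 to 16, so the 40% v 28% shift becomes 1.2 to 1.9 days.

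**Effect on the tests.** I simulated 3,000 trials per scenario at an assumed two-sided 5% level. Survivors' stay was the same in both arms (lognormal, median 18 days, sigma 0.4, capped at 30) and deaths were uniform over days 1 to 10.

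- At 40% v 28% with 50 per arm, the worse arm had the shorter mean stay in 84% of trials. It won significantly in 16.9% (Mann-Whitney) or 15.6% (t-test), against about 2.5% expected by chance. With 20 per arm the Mann-Whitney figure was 8.9%.
- At 26% v 18.2% with 50 per arm, the Mann-Whitney figure was 8.6%.
- At 40% v 28% with 50 per arm, spreading deaths to day 20 or day 30 cut the 16.9% to 9.7% or 4.2%.
- With equal mortality (40% in both arms, 50 per arm) it was 2.8% in each direction, so no bias.
- When deaths were ranked worst (40% v 28%, 50 per arm), significant results for the worse arm fell from 16.9% to 0.2%, and those for the better arm rose from 0.2% to 18.0%.

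**The case against.** The strongest reply is that the plan is silent, not wrong. A reader might infer that it counts early deaths as short stays, but no section says so. Counting them is only what happens if the column of days goes into the named tests as it stands. Kaplan-Meier and Cox are also promised and could be meant for time to discharge. This stands as to wording, but it does not remove the problem. The survival methods are tied to no outcome and have no competing-risk rule, and both simple ways of filling the gap (observed days, or survivors only) can mislead.

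A reader might also set 58% against 26% and obtain a shift of 0.32 × 12 to 14 = 3.8 to 4.5 days. The documents do not support that contrast. The two figures are the ends of one background range for severe lung failure, not rates for two adsorbers. That range resembles at most the pulmonary-failure ECMO subgroup, 20 of 100 patients. Half the trial is prolonged bypass surgery, and if the 7% quoted for SIRS is nearer for those patients, the shift is about 0.3 days. Even the 30% reduction is a hope for the programme, not a difference between devices. It only sets a scale.

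Extending the argument to ICU stay is also tempting. Read literally, that row has a window of the first 48 hours in all three tables, and a death on day 6 to 8 cannot shorten a stay measured within it.

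Finally, hospital stay is a third-tier outcome with survival listed directly below it, so a mortality difference would be visible to a careful reader. That limits the harm, but the stay result would still point the wrong way.

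**Conclusion.** The point holds as a conditional one. With no rule for deaths, the named tests on hospital stay can favour the device with more early deaths. Under the stated assumptions the false advantage is 0.9 to 1.1 days at 26% v 18.2%, 1.4 to 1.7 days at 40% v 28%, and about 0.3 days at 7% v 4.9%.

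The direction needs two things only: unequal mortality, and deaths earlier than survivors' usual discharge. The size rests on assumed stays and death days and on background mortality, because the documents give no expected values by arm. The gap should be closed before the data are analysed. Because of the outcome's rank, it does not by itself undermine the trial's main comparisons.

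The same gap reaches a primary result, however: in the ECMO table, total days on ventilation, vasopressors and renal replacement to day 30 (primary row 6) also has no rule for deaths.

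**What to change.** In all three tables, compare days alive and out of hospital to day 30 from randomisation, with any death within 30 days scored 0. Show stay among survivors descriptively, without a test, and keep 30-day survival beside it.

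Apply the same rule to ECMO primary row 6, as days alive and free of each support to day 30. Apply it to ICU stay only after the 48-hour window in that row has been reconciled with a length-of-stay measure.

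**Cost.** Most of this is SAP wording, but it also needs data: dates of randomisation, discharge, readmission and death to day 30. A reader might assume these are already collected, but section 4 lists durations and survival, not dates. Time zero must also be aligned, since ECMO primary row 6 counts from surgery.

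**Downside.** The measure combines death and stay, so its components must be reported separately. A survivor still in hospital on day 30 also scores 0, the same as a death. Ranking deaths as the worst outcome is a workable alternative if many patients are expected to stay that long.
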